2.2 Analysis sets

The following analysis populations will be used for analysis.

- The Enrolled population will include all patients who were enrolled into the study.
- The Full Analysis Set (FAS) will include all patients randomized. Mis-randomized patients will be excluded from the FAS.
- The modified Full Analysis Set (mFAS) will include all patients who could have completed Week 12 by the study termination date. That means, all patients which were randomized at least 12 weeks prior to 25-Feb-2019 will be included.
- The Safety population (SAF) will include all patients who took at least one dose of study medication and who had at least one post-baseline safety assessment.

The primary efficacy analysis will be the FAS.

2.3 Patient disposition, demographics and other baseline characteristics

Patient demographic and baseline characteristic data to be collected on all patients include: year of birth, age, sex, race, ethnicity, relevant medical history/current medical condition present before signing informed consent, height, weight, body mass index (BMI), prior concurrent medications, QTc using Fridericia's correction, NRS at screening, [REDACTED].

In addition, the following categorizations of continuous variables will be done:

- Age into 18-64 years, 65- 84 years, \geq 85 years
- Duration of PHN into $<$ 1 year, $>$ 1 - 5 years, $>$ 5 - 10 years, $>$ 10 - 15 years, $>$ 15 - 20 years, and $>$ 20 years;

Demographic and background information will be summarized for the FAS population using frequency distributions (for categorical variables) and descriptive statistics of mean, standard deviation, minimum, median and maximum (for continuous variables). Relevant medical history/current medical conditions will be summarized by system organ class and preferred term of the MedDRA dictionary.

2.3.1 Patient disposition

For each study phase (i.e., screening, treatment epoch and treatment withdrawal epoch), the overall number of patients who entered, completed, and discontinued that phase will be summarized including the reasons for discontinuation. The summary of the screening phase will be done for the Enrolled set, for the treatment and treatment withdrawal epoch the analyses will be based on the FAS population.

Patients who prematurely discontinue the study medication will be listed along with the reason for discontinuation.

2.4 Treatments (study treatment, rescue medication, concomitant therapies, compliance)

2.4.1 Study treatment / compliance

Duration (days) of exposure to double-blind study medication will be summarized by treatment group and treatment phase (treatment epoch and treatment withdrawal epoch separately). In addition, the number of subjects with exposure of at least certain time thresholds (any exposure, ≥ 1 week, ≥ 2 weeks, ≥ 4 weeks, ≥ 6 weeks, ≥ 8 weeks, ≥ 10 weeks, ≥ 12 weeks) will be displayed.

Compliance will be recorded as source documentation only and not analysed.

The analyses will be based on the SAF population.

2.4.2 Prior, concomitant and post therapies

The number and percentage of patients who used concomitant medications (coded by World Health Organization [WHO] Anatomic Therapeutic Chemical classification [ATC]) will be presented by treatment group and treatment phase (Treatment epoch and Treatment withdrawal epoch separately).

Separate tabulations will be provided for medications taken prior to start of study medication and while a patient is on study drug (i.e. concomitant, between the first day on study drug and the day of last visit). The PHN medications recorded on the Screening PHN Medication Log will be summarized using a frequency table for each medication. The primary reason for treatment failure will also be tabulated.

Prior medications are defined as drugs taken and stopped prior to first dose of study treatment. For the Treatment epoch concomitant medications are defined as any medication given at least once between the day of first dose of study treatment and the end of the treatment epoch, including those which were started pre-baseline and continued into the treatment period. For the Treatment withdrawal epoch concomitant medications are any medications given at least once between the day of first dose of study medication in the treatment withdrawal epoch, and the end of the epoch, including those which were started pre-baseline or in the treatment period epoch, and continued into the treatment withdrawal epoch.

Non-drug therapies will be listed.

2.4.2.1 Rescue medication

The number and percentage of patients who received rescue medication (Acetaminophen/Paracetamol as reported on the diary page) will also be summarized by treatment and by visit during the double blind and treatment withdrawal period separately. Visit mapping will be done according to the visit window strategy document. The dose received will be listed.

Analysis of time to first use of rescue medication will be performed using Kaplan-Meier curves. Number of patients with at least one intake will also be summarized.

2.5 Analysis of the primary objective

2.5.1 Primary endpoint

The primary efficacy variable will be the change from baseline to Week 12 in the weekly mean of the 24-hour average pain score, using an 11-point Numeric Rating Scale (NRS).

The NRS is captured in the e-diary daily by the patient as the intensity of pain in the past 24 hours. To calculate the weekly mean pain intensity score for a given week, the daily pain intensity scores collected by the patient in the e-diary during the 7 days of that week will be averaged.

The primary population will be the FAS.

2.5.2 Statistical hypothesis, model, and method of analysis

The aim is to estimate the treatment effect of the investigational drug (EMA401) compared to placebo, for the target population on the primary pain parameter. The definition and the justification of the corresponding primary estimand, as well as the definition of the supplementary and secondary estimands are detailed in the Estimand Charter.

The primary estimation method is based on an Analysis of Covariance (ANCOVA) model including region (America or Europe and Australia, Asia), treatment, sex, use of concomitant pain medication for PHN (yes/no) as factors and age and baseline (mean pain intensity) score as covariate. The analysis will account for different intercurrent events (i.e. events that occur post-randomization) as follows:

- **Changes in doses of concomitant medication for PHN:** Efficacy observations collected during the period of changes in doses of concomitant medication for PHN (compared to baseline) and the 2-days thereafter will be excluded, since they are considered affected by the concomitant medication dose change. The resulting missing data after this step will be multiply imputed using the Missing at random (MAR) assumption.
- **Intake of rescue medication:** Efficacy data collected during intake of rescue medication will be used for analysis.

- **Intake of prohibited medications with potential confounding effect prior to study treatment discontinuation:** The prohibited medications with a potential confounding effect are defined as those listed in Table 2-1 requiring study treatment discontinuation. A list of prohibited medications is available at the following [REDACTED]

[REDACTED] Efficacy

observations collected during the intake period of such prohibited medications and the 7-days thereafter will be excluded, since they are considered affected by the prohibited medication intake. The resulting missing data after this step will be multiply imputed using the MAR assumption.

Table 2-1 Prohibited medication

Medication	Prohibition period	Action taken for study treatment
Prohibited prior to Randomization and throughout study		
High dose capsaicin patch (8%)	3 months prior to Randomization and after Randomization	Discontinue study treatment
Prohibited 2 week prior to Randomization and throughout the study		
Any skeletal muscle relaxant (e.g. baclofen, orphenadrine, methocarbamol)	2 weeks prior to Randomization and after Randomization	None
Mexiletine	2 weeks prior to Randomization and after Randomization	None
Dextromethorphan	2 weeks prior to Randomization and after Randomization	None
Memantine	2 weeks prior to Randomization and after Randomization	None
Alpha-lipoic acid	2 weeks prior to Randomization and after Randomization	None
Other anti-epileptic drugs (e.g. valproic acid, carbamazepine, phenytoin)	2 weeks prior to Randomization and after Randomization	Discontinue study treatment upon 2 nd episode of medication use
Oral or injectable steroids	2 weeks prior to Randomization and after Randomization	Discontinue study treatment upon 2 nd episode of medication use
Monoamine oxidase inhibitors or any other antidepressants (except stable dosage of SSRI)	2 weeks prior to Randomization and after Randomization	Discontinue study treatment upon 2 nd episode of medication use

Medication	Prohibition period	Action taken for study treatment
Antipsychotic or neuroleptic medications	2 weeks prior to Randomization and after Randomization	Discontinue study treatment upon 2 nd episode of medication use
Cannabinoids (e.g. marijuana)	2 weeks prior to Randomization and after Randomization	Discontinue study treatment upon 2 nd episode of medication use
Prescribed opioids, including codeine	2 weeks prior to Randomization and after Randomization	Discontinue study treatment upon 2 nd episode of medication use
Any prescription systemic pain medication, or topical treatment for PHN, including lidocaine plaster	2 weeks prior to Randomization and after Randomization	Discontinue study treatment upon 2 nd episode of medication use
Nonsteroidal Anti-inflammatory Drugs (NSAIDs) or any other over-the-counter pain medications	2 weeks prior to Randomization and after Randomization	None
Any non-drug therapies that could modulate the perception of pain either directly or indirectly (i.e. transcutaneous electrical nerve stimulation (TENS) or surgery)	2 weeks prior to Randomization and after Randomization	Discontinue study treatment
Other medications that may have potential drug-drug interactions (e.g. felodipine, eplerenone, nisoldipine, ticagrelor, tacrolimus, avasimibe, rifampin, cyclosporine, gemfibrozil, clarithromycin, St. John's Wort; oral, injected or implanted hormonal methods of contraception), Antiviral medications (e.g. valacyclovir, acyclovir, amantadine, anti-HIV), Antifungals (e.g. Azoles)	2 weeks prior to Randomization and after Randomization	None
Prohibited after Randomization and throughout study		
Any change to a different standard of care medication from baseline (e.g. switch from pregabalin to gabapentin) will be treated as prohibited medication	After randomization	Discontinue study treatment

Retrieved drop-out (RDO) patients are defined as patients who discontinue study treatment and decide to remain in the study by following an abbreviated schedule of assessments. These patients must continue to adhere to protocol requirements (see respective protocol Table 6-2). The design feature of retrieved drop-outs, considered in order to minimize the occurrence of missing data on primary pain parameter, is exploited for the statistical analysis as follows:

- **Permanent discontinuation of study treatment due to AE, lack of efficacy (LoE) and use of prohibited medication:** If retrieved drop-out data are available, these will be used for analysis. If no data was retrieved after study treatment discontinuation, missing data

will be multiply imputed based on placebo arm data, i.e. “jump to reference” (J2R) assumption for the EMA401 arms, missing at random assumption for placebo arm (Carpenter, Roger, and Kenward 2013). If no RDO data was collected after study treatment permanent discontinuation, missing data will be multiply imputed based on the J2R assumption for the EMA arms and under the MAR assumption for placebo arm. Of note, alternatively one could build the imputation model based on the RDO data, however, we expect sparse RDO data which will likely hinder us to build an imputation model. More details on the imputation model are specified in Section 5.

- **Permanent discontinuation of study treatment due to other reasons than AE, LoE and use of prohibited medication (including discontinuation due to USM):** If efficacy data collected after study treatment discontinuation are available (retrieved drop-out), then the retrieved drop-out data will be excluded and missing data after study treatment discontinuation will be multiply imputed using the MAR assumption.

The multiple imputations will be carried out on the weekly mean pain score. Details on multiple imputation can be found in Section 5 of this document.

If the 300 mg b.i.d dose would have been initiated: The primary objective would have been achieved if the null hypothesis of flat dose-response curve (where all dose means are equal to the placebo mean) at Week 12 is rejected using $\alpha=0.025$ one-sided. The null hypothesis of a flat dose-response curve will be tested using Multiple Comparison Procedure – Modelling (MCP-Mod) with three E_{\max} and two sigmoidal- E_{\max} dose response models as the candidate shapes. The following ED_{50} (the dose at which half of the maximum effect is reached) values will be used for the E_{\max} models: 17, 80, and 200. The parameters of the sigmoidal E_{\max} models (ED_{50} , h) will be as follows: (77, 3) and (175, 1.5), where h is the Hill parameter that determines the steepness of the dose-response shape. The MCP-Mod dose response test will be performed at each post-baseline visit. No multiplicity adjustment by visit will be carried out.

Dose-response estimation will be performed based on the ANCOVA least square estimates using MCP-Mod as described in Pinheiro et al (2014). The same candidate models as above will be used in a model averaging approach to obtain an estimate of the dose-response curve. The final estimate of the dose-response curve is the median of the dose-response curves obtained.

The same ANCOVA model will be applied at the visits prior to Week 12.

Summary statistics for absolute values and change from baseline by treatment and visit will be provided for the original measurements (i.e. the raw data prior to multiple imputation) of the primary efficacy variable. If a measurement is collected under the period of use of prohibited medications or the 7 days thereafter, it will be excluded from the summaries. [REDACTED]

In the event the EMA401 300 mg b.i.d. dose cannot be initiated, the trend tests deduced from the set of candidate models will be performed but the dose response estimation will not be performed. In that case, the first secondary objective will be evaluated to compare the efficacy of the remaining doses of EMA401 over placebo in 24-hour average pain intensity score at Week 12, using an 11 point Numeric Rating Scale (NRS). This comparison will be done by

testing the null hypotheses of superiority of EMA401 25 mg b.i.d. over placebo and of EMA401 100 mg b.i.d. over placebo, while adjusting for multiplicity. The estimation of the treatment difference and missing data handling will be performed using the method of analysis mentioned for the primary analysis. Multiplicity adjustment for the pairwise comparisons will be performed using the Hochberg procedure. To facilitate the interpretation of the estimated treatment difference a standardized effect size will be provided and will be calculated based on the results of the ANCOVA analysis.

2.5.3 Handling of missing values/censoring/discontinuations

Handling of missing daily pain score values within a week (within-week imputation)

The 24-hour average pain score is measured daily for seven consecutive days prior to randomization and then every day through the end of the study. At each week, the weekly mean of the seven 24-hour average pain assessments will be calculated.

The weekly mean will be calculated based on the available assessments. If only one measurement is available, the mean will be based on that value. Assessments made under treatment will not be mixed up with RDO data. If there is at least one value among the seven values in one week which is on-treatment (i.e. collected prior to study treatment discontinuation), the mean will be calculated based on those on-treatment values. If all seven values in one week are off-treatment because collected after study treatment discontinuation (RDO), the resulting weekly average will be regarded as an RDO value for analysis.

Handling of missing weekly mean pain score values (weekly mean imputation)

The multiple imputation for the primary variable will be carried out on the weekly mean pain score.

The imputation procedure related to primary analysis is described in Section 2.5.2 while the imputation procedure for the supplementary analyses is included in Section 2.5.4. The details of these imputation rules are specified in the Estimand Charter and in Section 5.

For all analyses, imputation of intermittent missing observations before treatment discontinuation will be carried out following a MAR mechanism for all treatment arms.

2.5.4 Supportive analyses

2.5.4.1 Supplementary analysis

The following supplementary analysis to the primary analysis will be performed on the FAS population

to quantify the treatment effect of the investigational drug compared to placebo, that would have been observed had all patients remained on their assigned treatment for 12 weeks. The handling of post randomization events will be same as for the primary analysis, except that missing data after discontinuation for any reason in both treatment arms will be imputed using the MAR assumption.

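### The one retained supplementary analysis targets the effect with everyone on treatment but, as written, keeps off-treatment scores after AE, lack-of-efficacy and prohibited-medication stops

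*SAP*

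**What the plan says.** SAP 2.5.4.1 describes the only supplementary analysis of the primary endpoint kept after Amendment 1. Its target is the effect "that would have been observed had all patients remained on their assigned treatment for 12 weeks". The Amendment 1 rationale gives the same purpose: the improvement if every patient could take EMA401 as prescribed for 12 weeks. The rule reads "The handling of post randomization events will be same as for the primary analysis, except that missing data after discontinuation for any reason", and such data are then imputed under MAR in both treatment arms. Protocol 9.4.4 words its second supplementary analysis in the same way.

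The primary handling that this inherits is in SAP 2.5.2, which separates two kinds of permanent stop:

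- **Adverse event, lack of efficacy, prohibited medication:** "If retrieved drop-out data are available, these will be used for analysis". Only if nothing was retrieved are values imputed, by jump to reference in the EMA401 arms and MAR on placebo.
- **Any other reason, including the urgent safety measures (USM):** "then the retrieved drop-out data will be excluded and missing data after study treatment discontinuation will be multiply imputed using the MAR assumption".

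SAP 2.5.3 adds that when all seven days of a week are off treatment, "the resulting weekly average will be regarded as an RDO value for analysis". It also says that "the imputation procedure for the supplementary analyses is included in Section 2.5.4", with details in the Estimand Charter and SAP Section 5.

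**The concern.** The exception in 2.5.4.1 concerns missing data only. A retrieved drop-out (RDO) score recorded after a stop for an adverse event, lack of efficacy or prohibited medication is not missing, and the inherited rule says to use it. Read literally, some Week 12 values in an analysis of continued treatment would come from patients no longer taking the drug.

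The result is also uneven: an off-treatment score would be removed after a USM stop and kept after an adverse-event stop, although neither belongs to the target. For first-category patients with a Week 12 RDO score, the primary and supplementary analyses would use the same observed value, although the supplementary analysis exists to answer a different question.

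The rule reaches beyond the pain score. SAP 2.7.3 applies the same supplementary analysis to the NPSI total score, which Protocol Table 6-2 collects after discontinuation. SAP 2.7.2 also carries it to a supplementary responder estimand, although SAP Section 4 lists supplementary responder analyses among those dropped.

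**Working it through.** **1. What happens to each stop**

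| Stop and data | Primary (SAP 2.5.2) | Supplementary as written (SAP 2.5.4.1) | What the target needs |
|---|---|---|---|
| AE, lack of efficacy, prohibited medication; RDO score present | Score used | No change stated: score used | Exclude, then MAR |
| Same reasons; no RDO score | Jump to reference (EMA401), MAR (placebo) | MAR | MAR |
| Other reasons including USM; RDO score present | Exclude, then MAR | Exclude, then MAR | Exclude, then MAR |
| Other reasons including USM; no RDO score | MAR | MAR | MAR |

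Only the first row fails. Where the SAP wants collected scores removed, it says so as a separate step before imputation: for dose changes of PHN medication, for prohibited-medication intake before discontinuation, and for other-reason stops. SAP 2.5.4.1 has no such step. SAP 5.5.1.2, which builds the MAR model on available data from the same arm, does not supply one.

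**2. Size**

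The plan gives no figure for this analysis. (Its power statement of at least 77% reproduces, with a minimum of 77.1% over the five candidate shapes, but does not bear on this point.)

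Inputs:
- 129 patients randomized (SAP, Amendment 1 rationale), 1:1:1. Taken as exact, n = 129/3 = 43 per arm.
- SD 2.0 observed in Study EMA401-003 and 2.6 for planning (SAP Section 3).
- d = off-drug minus on-drug mean score. Assumption: off-drug patients score like placebo, with the four-week difference at 100 mg b.i.d. from Protocol 3.3.1: d = 2.29 − 1.60 = 0.69. There is no figure for 25 mg b.i.d.

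Standard error of a pairwise difference, unadjusted and with complete data: SE = SD × √(2/43), giving 0.431 at SD 2.0 and 0.561 at SD 2.6.

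Shift in an EMA401 arm mean with k affected patients: k × d/43.

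| k | Shift (points) | % of SE, SD 2.0 | % of SE, SD 2.6 |
|---|---|---|---|
| 1 | 0.016 | 3.7 | 2.9 |
| 2 | 0.032 | 7.4 | 5.7 |
| 3 | 0.048 | 11.2 | 8.6 |

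If 10% stop for these reasons and 30% of them have a Week 12 RDO score (both assumed), k = 0.10 × 0.30 × 43 = 1.29 and the shift is 0.021 points (4.8% or 3.7% of the SE). A shift of 0.10 would need 0.10 × 43/0.69 = 6.2 patients in one arm.

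The same model over a wider range: with stopping share f and retrieved share g, a true difference of 0.69 becomes 0.69 × (1 − f × g). That is 0.68 for f = 5%, g = 25%; 0.66 for 10% and 50%; and 0.55 for 20% and 100%. The last case fits poorly with the SAP's own expectation: "we expect sparse RDO data which will likely hinder us to build an imputation model". In addition, 25-Feb-2019 minus 12 weeks is 3-Dec-2018, so patients randomized after that date could not reach Week 12 by the termination date.

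**3. Direction**

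Protocol 5.6.2 provides for care after stopping in all arms, within limits: "These patients must continue to adhere to protocol requirements". Let that care lower pain by c in every arm, with RDO shares fE (EMA401) and fP (placebo). The EMA401-minus-placebo difference then moves by fE × (d − c) + fP × c. If fE = fP = f, this is f × d and c cancels; with d = 0 as well, it is zero. If the shares differ, the sign depends on c, and the shares are not documented.

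**The case against.** The strongest reply is that the SAP delegates this question. Section 2.5.2 says the supplementary estimands are defined in the Estimand Charter, and 2.5.3 points there for imputation details. The Charter may exclude RDO data, in which case 2.5.4.1 is only an incomplete summary. This stands as a limit on what can be said about intent. It does not change what the SAP text says, and 2.5.3 itself names 2.5.4 as the place for the procedure.

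Second, a reading that fits the target exists. In the other-reasons rule, the data described as missing after discontinuation include scores made missing by exclusion; 2.5.4.1 uses nearly the same phrase for every reason. This is a fair reading, but it requires the reader to supply an exclusion step that the SAP writes out elsewhere. Two programmers could reasonably differ.

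Third, two passages carry little weight. The 2.5.3 sentence on fully off-treatment weeks only classifies a value: it applies equally to other-reason stops, whose values are then excluded. The reference in 5.5.1.2 to available data is qualified by scheduled time points, so it concerns visits, not RDO status. Both points are right. The finding does not need either passage to say that scores are retained; it needs only that neither removes them.

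Fourth, d is a rough stand-in. MAR imputation uses a patient's own earlier scores, so the exact quantity is the RDO score minus that patient's imputed value. This also stands: the figures are first-order and leave out any effect of RDO scores on the imputation model.

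Finally, the effect is small and the trial was terminated early. That bears on priority, not on whether rule and target agree.

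**Conclusion.** The concern holds on the wording: in SAP 2.5.4.1 and Protocol 9.4.4 the stated rule does not deliver the stated target for patients with RDO scores after an adverse-event, lack-of-efficacy or prohibited-medication stop. Confidence is medium, because the Estimand Charter could not be read.

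The numerical effect is likely small: about 0.02 points in the illustrative scenario and under 0.05 points for up to three affected patients in an arm. This rests on 43 patients per arm, off-drug scores that follow placebo with d = 0.69, and assumed stopping and retrieval shares. The direction is not established. The primary analysis and the handling of USM stops are not affected.

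It should be fixed because this is the only supplementary analysis of the primary endpoint left, its interpretation depends entirely on the on-treatment condition, and its NPSI counterpart inherits the rule.

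**What to change.** Before unblinding, add to SAP 2.5.4.1 a sentence to this effect: all scores after permanent study treatment discontinuation for any reason, including retrieved drop-out data, are excluded from this analysis and from its imputation model; the resulting missing weekly means are imputed under MAR from on-treatment data of the same arm.

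Apply the same rule to the supplementary NPSI analysis in SAP 2.7.3, and to the supplementary responder analysis in 2.7.2 if it is still to be performed. Check that the Estimand Charter agrees. If the Charter shows that keeping RDO scores was intended, the stated target should be changed instead.

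The cost is one sentence, one document check, and extending to every discontinuation reason an exclusion that the SAP already specifies for other-reason stops. No further data are needed. The documents do not show how far programming has gone.
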